8.3.1 Adjustment of NIMP

The dose of the mealtime insulin analogs (glulisine, lispro or aspart) will be titrated to achieve a target of 2-hour postprandial plasma glucose. The dose adjustment regimen can be titrated based on a pattern of postprandial plasma glucose results of SMPG (simple titration) OR based on the carbohydrate content of the meal (carb counting).

- The titration goal is a 2-hour postprandial SMPG in the range of 130 and 180 mg/dL (7.2-8.9 mmol/L) while avoiding hypoglycemia. For the purpose of this protocol, 2-hour postprandial is defined as 2 hours after the start of the meal.
- While basal insulin doses are increased, mealtime insulin doses may be reduced to avoid daytime hypoglycemia as deemed appropriate by the investigator.
- Appropriate adjustment in mealtime insulin will continue throughout the entire treatment period (Week 0-16).

The two regimens are described in Table 2 and Table 3.

Table 2 - Simple titration: Titration of mealtime insulin based on a pattern of post-meal glucose (median 130</>180 mg/dL in the prior 3 days)

Mealtime dose of Insulin	Pattern of postprandial BG values <130 mg/dL ^a	Postprandial BG values >180 mg/dL ^a
≤10 U	Decrease dose by 1 U	Increase dose by 1 U
11-19 U	Decrease dose by 2 U	Increase dose by 2 U
≥20 U	Decrease dose by 3 U	Increase dose by 3 U

^a If more than 50% of the mealtime blood glucose (2-hour PPG) values for the week were above target.

Table 3 - Carbohydrate counting: Insulin-to-carbohydrate ratio group

Mealtime dose of Insulin	Pattern of postprandial BG values <130 mg/dL ^a	Postprandial BG values >180 mg/dL ^a
1 U/20 g	Decrease to 1 U/25 g	Increase to 1 U/15 g
1 U/15 g	Decrease to 1 U/20 g	Increase to 1 U/10 g
1 U/10 g	Decrease to 1 U/15 g	Increase to 2 U/15 g
2 U/15 g	Decrease to 1 U/10 g	Increase to 3 U/15 g
3 U/15 g	Decrease to 2U/15 g	Increase to 4 U/15 g

^a If more than one-half of the mealtime blood glucose values for the prior 3 days were above target.

Investigators will also be provided with an initial guideline of 1800/TDD as a correction factor to be used if applicable at the investigators' discretion.

The injection of the mealtime insulin analogs in relation to the meal intake will be done according to the individual habits of the patient prior to the study while following the instructions in the national product label.

Dietary modifications (eg, snacks) will be made by the Investigator, dietician or other medically qualified person based on his/her best judgment.

Starting recommendation 1 U to 15 grams carbs

Consider calculating insulin to carb (I:C) ratio = 500 / total daily dose (TDD) of insulin.

8.4 BLINDING PROCEDURES

As Toujeo and the control drug Lantus are distinguishable, this study is an open-label design. The day- time of injection is not blinded either. Administration of all forms of insulin glargine during the trial is to be open-label, and no attempt will be made to blind day-time of injection.

8.4.1 Compensation for lack of blinding

Despite the open-label administration of study insulins, assessment of outcomes, where possible, will be based on objectively collected data, which are assessments for blinded CGM (primary endpoint) and SMPG data. The SMPG data stored in the glucose meter will be uploaded to the site computer for the study staff to verify the diary entries that will be documented onto the eCRF to support the analyses of the 7-point SMPG profile and the confirmed hypoglycemia (secondary and other endpoints).

Neither the Investigator nor the Sponsor will have access to the individual data for the primary efficacy parameter (CGM records) obtained in each patient. However, the study team may review the data for the primary efficacy parameter in descriptive statistics with the name of the investigational medicinal product (IMP) treatment masked during data review meetings.

8.5 METHOD OF ASSIGNING PATIENTS TO TREATMENT GROUP

The Trial Supply Chain Manager compiles the batch number list and the Study Biostatistician provides the randomization scheme (including stratification, Section 11) to the centralized treatment allocation system (IVRS - Interactive Voice Response System /IWRS - Interactive web response system). Then, the IVRS/IWRS generates the patient randomization list according to which it allocates treatment arms to the patients.

- The treatment kits, open-label boxes identified with batch numbers, are allocated to the patients by the IVRS/IWRS using the treatment number of the boxes.
- At the screening visit the investigator or designee has to call the IVRS/IWRS to receive the patient number. The patient identification (patient number) is composed of 9-digit number containing the 3-digit country code, the 3-digit center code and the 3-digit patient chronological number (which is 001 for the first patient screened in a center, 002 for the second patient screened in the same center, etc).
- Randomization will be stratified by HbA1c obtained at the screening visit (<8.0%; ≥8.0%), Lantus (and other basal insulin analogs) injection at screening BID vs QD, current CGM use (yes/no) and mealtime insulin titration algorithm followed. For each region the IVRS/IWRS will be configured as to reach a minimum of 20% randomized patients per HbA1c strata.
- On V3 (D1), for first treatment kit(s) allocation, the investigator or designee has to call the IVRS/IWRS to provide some information (such as patient number provided by IVRS/IWRS at screening visit, date of birth, etc). Afterwards the IVRS/IWRS is called again each time a new treatment kit(s) allocation is necessary, ie, the visits as indicated in the study flowchart (Section 1.2).

- A randomized patient is a patient who has been allocated to a randomized treatment regardless whether the treatment kit was used or not (ie, patient registered by the IVRS/IWRS).
- A patient cannot be randomized more than once in the study.

8.6 PACKAGING AND LABELING

Toujeo (insulin glargine 300 U/mL solution) is supplied for SC injection as a sterile, non-pyrogenic, clear, colorless solution in a 1.5 mL Toujeo SoloStar disposable prefilled pen (450 Units/1.5 mL).

Lantus (Insulin glargine) 100 U/mL solution) is supplied as insulin glargine solution for SC injection 100 U/mL in 3 mL cartridges assembled in a pen-injector.

Packaging is in accordance with the administration schedule. The content of the labeling is in accordance with the local regulatory specifications and requirements.

The respective number of the study treatment will be packaged under the responsibility of sanofi according to good manufacturing practice and local regulatory requirement. Toujeo will be supplied in boxes of 3 disposable pens for insulin glargine 300 U/mL and Lantus will be supplied in boxes of 5 disposable pens for insulin glargine 100 U/mL

8.7 STORAGE CONDITIONS AND SHELF LIFE

Investigators or other authorized persons (eg, pharmacists) are responsible for storing IMP in a secure and safe place in accordance with local regulations, labeling, specifications, policies and procedures.

Control of IMP storage conditions, especially control of temperature (eg, refrigerated storage) and information on in-use stability and instructions for handling the Sanofi compound should be managed according to the rules provided by the Sponsor.

The expiry date is mentioned on the IMPs labels, and storage conditions are written on the IMPs labels and in the instruction leaflet.

8.8 RESPONSIBILITIES

The Investigator, the hospital pharmacist, or other personnel allowed to store and dispense the IMP will be responsible for ensuring that the IMP used in the clinical trial is securely maintained as specified by the Sponsor and in accordance with applicable regulatory requirements.

All IMP will be dispensed in accordance with the Investigator's prescription and it is the Investigator's responsibility to ensure that an accurate record of IMP issued and returned is maintained.

Any quality issue noticed with the receipt or use of an IMP (deficiency in condition, appearance, pertaining documentation, labeling, expiration date, etc) should be promptly notified to the Sponsor. Some deficiencies may be recorded through a complaint procedure.

A potential defect in the quality of IMP may be subject to initiation of a recall procedure by the Sponsor. In this case, the Investigator will be responsible for promptly addressing any request made by the Sponsor, in order to recall IMP and eliminate potential hazards.

Under no circumstances will the Investigator supply IMP to a third party allow the IMP to be used other than as directed by this clinical trial protocol, or dispose of IMP in any other manner.

8.8.1 Treatment accountability and compliance

At each contact to the patient, either by phone or during on-site visit, the Investigator or his/her delegate has to ask the patient about administered doses of IMP (Toujeo or Lantus).

Returned and dispensed IMP will be documented into the Treatment Log Form. Investigator or delegate has to visually check the filling status of the cartridges in the pens in the returned packs and compare to dosing records documented in the patients' diaries. Discrepancies have to be addressed to the patient for clarification of real treatment administration. For unused IMP, pens will have to be stored accordingly.

The investigator completes the appropriate treatment log form based on the unused, used and inuse IMP (study drug pens) returned and records the dosing information on the appropriate page(s) of the e-CRF. However as type 1 diabetes patients are requiring insulin, the level of glycaemia as reflected by SMPG and HbA1c is a sensitive marker of adherence to insulin treatment.

The monitor will check the e-CRF data by comparing them with patient's diary entries, treatment log forms and unused treatment kits.

8.8.2 Return and/or destruction of treatments

Patients have to return all the used, in-use and unused IMP at each on-site visit except for the visit where re-supply is not planned (at this visit, unused pen will be left home) (or final assessment on treatment visit in case of permanent premature discontinuation).

8.8.2.1 IMP (Toujeo or Lantus)

All partially-used or unused treatments (inject devices with inserted cartridges; disposable Solostar pens) will be retrieved by the Sponsor. A detailed treatment log of the returned IMP will be established with the Investigator (or the pharmacist) and countersigned by the Investigator and the monitoring team.

The Investigator will not destroy any IMP unless the Sponsor provides written authorization. A detailed treatment log of the destroyed IMP will be established with the Investigator (or the pharmacist) and countersigned by the Investigator and the monitoring team.

A potential defect in the quality of IMP may initiate a recall procedure by the Sponsor. In this case, the Investigator will be responsible for promptly addressing any request made by the Sponsor, in order to recall IMP and eliminate potential hazards.

8.8.2.2 NIMP (mealtime insulin analogs)

As the mealtime insulin is not provided by the study sponsor, no NIMP return and destruction are required.

Patients have to record the administration of their mealtime insulin analog in the diary. ALL doses of mealtime insulin analogs during the day as taken for all meals and all snacks must be recorded. The sites have also to take care of source document of the NIMP in patient source documents and eCRF (NIMP name, dosage, daily total dose, injection compliance and dose-titration recommendation etc.) as specified in this protocol (Section 8.3).

8.9 CONCOMITANT MEDICATION

A concomitant medication is any treatment received by the patient concomitantly to IMP treatment. Any treatment which are continued during the study and/or initiated or changed during the study must be recorded in source data and in the e-CRF.

The IMP includes basal insulin of Toujeo and Lantus as the testing and control medications, respectively. Mealtime insulin analogs (glulisine, lispro or aspart) are the study required concomitant antidiabetic medication, which is defined as the NIMP in this study.

8.9.1 Prohibited medication during the study

During the study following medications are prohibited.

- Any antidiabetic agents other than the study medications mentioned above, including oral
 or injectable antihyperglycemic agents, other type of basal insulin (eg, NPH, Detemir, premixed insulin), and human regular insulin,
- Insulin pump therapy is not allowed during the course of the study,
- Initiation of any weight loss drugs is not allowed; previous treatment with weight loss drugs can be continued and doses must remain stable throughout the study,
- Systemic glucocorticoids for more than 10 consecutive days (topical or inhaled applications are allowed),
- Medications containing acetaminophen/paracetamol during the period of CGM performance as these medications can interact with the glucose sensor of the CGM device.

Other medications which are unlikely to interfere with the IMP and the study variables are allowed as needed and discussed with the investigator. However, doses of chronically administered medicines should be kept fixed during the trial if at all possible.

8.10 POSTSTUDY TREATMENT

Upon discontinuation of the study treatment, either scheduled or early permanent discontinuation with IMP, patients may either continue with their basal insulin during the study, both available in the market, or take a treatment alternate, approved form of basal insulin.

The choice of the basal insulin used after the end of study and dosing instructions are at the discretion of the treating physician. After the transition to post-study basal insulin, the doses of the new post-study basal insulin and the short-acting mealtime insulin should be adjusted based on SMPG data and prescribing information.

9 ASSESSMENT OF INVESTIGATIONAL MEDICINAL PRODUCT

9.1 PRIMARY ENDPOINT

The primary efficacy endpoint is the percentage (%) of time of glucose concentrations within the range of 70-180 mg/dL (3.9-10 mmol/L) during Week 15 (or 16), as obtained by CGM.

During Week 15, each patient will wear the CGM device for 7 consecutive days to generate at least 4 days of useable CGM records for the primary efficacy endpoint assessment. If a patient fails to provide at least 4 days (not necessarily consecutive) of useable CGM data over the 7-day CGM performance, he/she will repeat the CGM performance during Week 16.

- CGM data are blinded to both the patients and investigators,
- During the CGM performing week, the IMP insulin (Toujeo or Lantus) dose is fixed without a change, while the mealtime insulin dose can still be adjusted appropriately,
- Useable CGM data for a day are defined as at least 85% time of records without a gap (missing data) lasting for ≥ 2 hours per 24 hours. At least 4 days of qualified 24-h CGM records for each patient will be used for primary endpoint analyses,
- If a patient prematurely withdraws from the study before Week 15 (V18) the CGM data will be missing for the individual patient and the patient will be excluded from the primary efficacy analyses (see Section 11).

Further methods to handle missing data will be applied in the context of a sensitivity analysis and will be specified in the Statistical Analysis Plan (SAP).

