7.2.1 Exclusion criteria related to study methodology

- E 01. Age <18 years or >70 years
- E 02. Night shift worker,
- E 03. Use of investigational drug(s) within 1 month or 5 half-lives, whichever is longer prior to screening,
- E 04. Use of systemic glucocorticoids (excluding topical application or inhaled forms) for one week or more within 3 months prior to screening,
- E 05. Likelihood of requiring treatment during the study period with drugs not permitted by the study protocol (eg, acetaminophen/paracetamol during CGM period) and refusing to take alternative treatment,
- E 06. Mental condition rendering the patient unable to understand the nature, scope and possible consequences of the study and to perform blood glucose monitoring requirements, including the documentation of SMPG data and insulin dosing, or evidence of an uncooperative attitude and/or inability to return for follow-up visits, and unlikely to complete the study,
- E 07. Patients with severe unstable hepatic, gastrointestinal, cardiovascular (including congestive heart failure NYHA III/IV), respiratory, neurological, psychiatric, hematological, renal, endocrine, dermatological disease, active malignant tumor, other major systemic disease or patients with short life expectancy or any other medical condition that might interfere with the evaluation of study medication according to investigator's medical judgment,
- E 08. Hemoglobinopathy or hemolytic anemia, transfusion of blood or plasma products within 3 months prior to screening,

- E 09. History of drug or alcohol abuse within 6 months prior to screening,
- E 10. Pregnant or breast-feeding women or women who intend to become pregnant during the study period as glycemic control may be unstable and insulin doses may be variable during this period,
- E 11. Patients unable to speak, read and write,
- E 12. Patient is the Investigator or any subinvestigator, research assistant, pharmacist, study coordinator, other staff or relative thereof directly involved in the conduct of the protocol.

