10.2.4.2 CGM qualification and data transfer

After Visit 2 and Visit 18, each patient will wear the CGM for 7consecutive days to generate a minimum of 4 days (not necessarily to be consecutive) of usable CGM records. One day of qualified CGM data is defined as \geq 85% recorded time over 24 hours without a gap lasting for \geq 2 hours.

Next visits (Visit 3 and Visit 19) will occur after 7 days of CGM performance. If a patient cannot come for the site visit as scheduled he/she should inform the site immediately, as the CGM device will be automatically turned off. The patient may remove the sensor/transmitter by themselves at home or keep the "expired sensor" in place and remove it later during the site visit. Patients must bring the CGM device to the site at Visit 3 and Visit 19. The CGM will be uploaded into the study computer with and a report summary with daily CGM performance will be available immediately. Investigators will not be able to see the recorded glucose values, nor will the report include any real glucose data. The CGM summary will be used for the investigators to review the patient's daily performances and determine the quality of CGM.

Investigators must review and print out the summary (to be source documents). One day of CGM record is considered as qualified and useable if it meets follows:

- the daily performance hours are marked as 24 hours ie, a record of <24 hours does not count for a day
- the percentage of captured records is ≥85% of time (calculated by the system) over 24 hours
- during the 24 hours of a day, there is no gap (missing records) lasting for ≥ 2 hours

Only patients with 4 days of above qualified CGM records that are indicated in the CGM report will proceed to randomization or end-of-treatment. If for any reason, a patient fails to complete the qualified CGM, he/she will repeat the course of CGM. In such a case, all efforts should be made to help the patient find the root-cause of the failure and succeed in the next attempt.

In such a case, completion of procedures at Visit 3 for randomization or Visit 19 for the end of treatment will be postponed.

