11.4.2 Analyses of efficacy endpoints

11.4.2.1 Analysis of primary efficacy endpoint(s)

The percentage of time plasma glucose within target range of 70-180 mg/dL (3.9–10 mmol/L) during Weeks 15-16 (obtained from CGM) will be calculated based on the total time within glycemic range in the evaluable assessment interval, divided by the total time of the evaluable assessment interval.

The evaluable assessment interval for the calculation will comprise of 24-hour periods during Weeks 15-16 for which there is sufficient non-missing data. In order to be evaluable for analysis, a patient needs at least 4 days of 24-hour data meeting this criterion and should not receive protocol prohibited medication.

The endpoint will be summarized by treatment group using mean, median, standard deviation, minimum and maximum.

Differences between treatment groups will be explored using a generalized linear model, adjusting for key baseline characteristics (duration of diabetes, BMI, age and baseline value) and randomization strata. Adjusted mean estimates for each treatment with standard errors, the adjusted estimate of treatment mean difference with standard error and a 95 % confidence interval for the treatment mean difference will be provided. The statistical test will be for superiority of Toujeo over Lantus, two-sided and at a 5% significance level.

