2.1.3 Efficacy endpoints

The baseline value for efficacy parameters is defined as the last available value before the first injection of IMP.

Baseline CGM measurements will start at Visit 2 and stop at randomization visit (Visit 3).

Observation period for efficacy endpoints

- The on-treatment period for efficacy variables is defined as the time from the first dose of IMP up to:
 - Seven (7) days after the last dose of IMP for HbA1c,
 - One (1) day after the last dose of IMP for hypoglycemia,
 - One (1) day after the last dose of IMP for FPG, SMPG and CGM,
 - Zero (0) day after the last dose of IMP for insulin glargine dose.
- The randomized period for efficacy variables is defined from the first dose of IMP up to Week 16 (visit 19).

All efficacy parameters will be performed on on-treatment period and randomized period.

All CGM derived variables will be subject to the following criteria.

1. CGM data are blinded to both the patients and investigators.
2. During the CGM performing week, the IMP insulin (Toujeo or Lantus) dose is fixed without a change, while the mealtime insulin dose can still be adjusted appropriately.

3. A complete 24-hour CGM profile includes 288 data points given that CGM reading is recorded every 5 minutes.
4. The start and end time of a 24-hour CGM profile is defined as midnight. i.e. each CGM profile begins at midnight (hour 0) and ends at midnight (hour 24 = hour 0). Partial CGM data points prior to the first midnight and after the last midnight from the visit will not be used in the CGM parameter calculation as the partial CGM profile may introduce additional variabilities to the data.
5. Useable CGM data for a day/a 24-hour CGM profile are defined as at least 85% time of records (245 data points) without a gap (missing data) lasting for ≥ 2 hours per 24 hours. At least 4 days of qualified 24-hour CGM records for each patient will be used for efficacy analyses. If the partial CGM data described in previously have at least 85% of a full CGM profile or 245 data points, the partial CGM profile will be used to calculate CGM parameters.
6. In cases that there are more than 288 data points or more than one data point per 5 minutes, usually due to recalibration or switching CGM devices, it will be reviewed and treated case by case. Usually averaging the data points every 5 minutes will be performed so that there is only one data point per 5 minutes.

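### The CGM day-qualification test checks only completeness while acetaminophen is handled only by a patient-level clause, so patients who had, or could have repeated to get, four clean days can be lost.

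*Protocol*

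**What the plan says.** **Day-level test.** It appears in three places.
- Protocol 9.1: "Useable CGM data for a day are defined as at least 85% time of records without a gap" lasting 2 hours or more.
- Protocol 10.2.4.2: "One day of CGM record is considered as qualified and useable if it meets follows", followed by three conditions: a full 24-hour record, at least 85% captured, and no gap of 2 hours or more.
- SAP 2.1.3 item 5: "Useable CGM data for a day/a 24-hour CGM profile are defined as at least 85% time of records (245 data points) without a gap" of 2 hours or more. SAP 2.4.4.1 refers to this section for both baseline and Week 16 CGM.

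None of the three mentions medication.

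**What the day count controls.** Protocol 10.2.4.2: "Only patients with 4 days of above qualified CGM records that are indicated in the CGM report will proceed to randomization or end-of-treatment". Patients who fall short repeat the CGM course.

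**Acetaminophen.** Protocol 8.9.1 lists among prohibited drugs: "Medications containing acetaminophen/paracetamol during the period of CGM performance as these medications can interact with the glucose sensor of the CGM device". SAP 2.1.2 repeats this. Exclusion E 05 gives the same drug as its example ("eg, acetaminophen/paracetamol during CGM period") but excludes only likely users who refuse an alternative.

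**Patient-level clause.** Protocol 11.4.2.1 says that, to be evaluable, "a patient needs at least 4 days of 24-hour data meeting this criterion and should not receive protocol prohibited medication". SAP 2.4.4.1 repeats the clause. The mITT definitions in Protocol 11.3.1.1 and SAP 2.3.1.1 do not; they ask only for an assessment or for enough data.

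**The concern.** The plan names one drug that can interact with the sensor, yet the test of whether a CGM day is fit for use does not ask about it. The question arises only at analysis, when the repeat week is no longer available.

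The site cannot notice the problem at the visit. The CGM summary shows capture and gaps but no glucose values (Protocol 10.2.4.2). The needed information is at hand, because the flow chart has concomitant medication recorded at Visits 3 and 19.

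At stake are randomized patients who drop out of the primary analysis although they had enough unaffected days or could have obtained them. So is a primary dataset that two analysts could build differently: one following the evaluability clause, the other the mITT definition.

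**Working it through.** **1. The plan's own power figure.** Inputs from Protocol 11.1: difference 4 points, SD 14 points, two-sided 5% t-test, 262 evaluable per arm. The noncentrality is 4 / (14 × √(2/262)) = 3.27, which gives power 90.4%. The stated figure of at least 90% reproduces. At 259 per arm power is 90.1%, and at 258 it is 89.96%.

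**2. The two rules applied to the same patient.** Sensor insertion takes place at a visit and SAP 2.1.3 item 4 counts days from midnight to midnight, so a 7-day wear gives about 6 full days.

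| Case | Day-level test | Evaluability clause, read as exclusion | If affected days were not usable |
|---|---|---|---|
| Visit 19: 6 complete days, 1 affected | 6 days, passes | patient non-evaluable | 5 clean days, patient kept |
| Visit 19: 4 complete days, 1 affected | 4 days, no repeat | patient non-evaluable | 3 clean days, repeat triggered |
| Visit 3: 4 complete days, 1 affected | 4 days, randomized | unclear whether it covers baseline | 3 clean days, repeat before randomization |

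In the third case, under SAP 2.1.3 the affected day enters the baseline covariate. If the clause does reach back to baseline, the site has randomized a patient who is already non-evaluable.

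**3. Other CGM endpoints.** SAP 2.1.3 applies its nine criteria to all CGM variables, and none concerns medication. The clause stands only in the primary-endpoint section, so nothing clearly carries it to the secondary and other CGM endpoints.

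**4. Illustrative size if affected days are kept.** Assumptions, none of them from the documents: 2% to 10% of patients affected, and time in range on one day of 4 to 7 shifted by 5 to 20 points.
- *Equal use in both arms.* The largest case is 10% of patients with a 20-point shift on 1 of 4 days, or 5 points per affected patient. The SD becomes √(14² + 0.10 × 0.90 × 5²) = 14.08 and power is 90.1%. Across the whole range power is 90.1% to 90.4%.
- *Use in one arm only.* The bias runs from 0.02 × 5/7 = 0.01 points to 0.10 × 20/4 = 0.5 points, against the assumed 4-point difference.

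**5. Illustrative size if patients are lost.** Suppose 2%, 5% or 10% of the 262 per arm were lost in addition to the planned allowance. That leaves 256, 248 or 235 per arm, and t-test power of 89.7%, 88.8% or 87.1%. Protocol 11.1 expects the adjusted model to do better than the t-test. With an assumed baseline correlation of 0.3, the SD is 14 × √(1 − 0.09) = 13.36 and the same numbers give about 92%, 91% and 90%.

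**The case against.** The strongest reply is that the plan does deal with acetaminophen in the primary analysis. The clause is in both documents, the drug is on both prohibited lists, E 05 keeps out likely users who refuse an alternative, and SAP 2.2 tabulates major deviations that could affect efficacy. This stands in part. A reader might infer from the day-level test alone that a distorted day simply counts in the primary endpoint. The documents do not support that as a flat statement, because on its natural reading the clause drops the patient. It does not answer the point that the drop could have been avoided at Visit 19.

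Three other stronger readings are tempting and also go too far.
- *The plan calls these readings invalid.* It says only that the drugs can interact with the sensor.
- *Affected readings are always used at baseline.* The clause has no stated time limit, so its reach to baseline is ambiguous. Baseline use also precedes randomization, so knowledge of the assigned arm cannot influence it.
- *The trial loses its 90% power.* No use rate is given, and 262 is already described as the evaluable number, so such losses may sit within the 15% allowance (308 × 0.85 = 261.8), although SAP 1.3 calls that allowance drop-out. The planned covariate adjustment also offsets some loss.

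It is also fair to object that one patient's worst-case error should not be set against a difference between group means. Averaged over an arm the shift is small, as step 4 shows.

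Finally, a bare rule by calendar day would miss a late-evening dose that carries past midnight, would conflict with the evaluability clause unless that is amended, and needs intake dates that SAP 2.5.3 does not impute. All three objections stand, and the fix has to meet them.

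**Conclusion.** The concern holds as a misalignment between two rules. The check that gates randomization and the repeat course looks only at completeness. The clause that deals with acetaminophen works per patient, comes after the repeat week has passed, and leaves three things open: whether it removes the day or the patient, whether it covers baseline, and whether it covers the other CGM endpoints.

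The size is unknown, because the documents give no use rate, error size or duration. Under the stated assumptions the group-level effect of keeping affected days is small: power of 90.1% to 90.4% with equal use, and at most 0.5 points of bias with use in one arm only. The main cost is avoidable loss of randomized patients from the primary analysis. Whether that takes power below 90% depends on an unknown rate, on whether such losses are already in the 15%, and on the gain from the baseline covariate. The change is worth making because it is cheap and leaves one primary dataset, not because the primary result is shown to be at risk.

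**What to change.** 1. In Protocol 9.1, Protocol 10.2.4.2 and SAP 2.1.3 item 5, add that a day with recorded acetaminophen/paracetamol intake is not usable. Pre-specify the affected window so that a late dose also removes the following day. The documents give no duration of interference, so the sponsor must supply and justify one.
2. State a rule for missing or partial intake dates. For example, the site queries the patient at the visit, and if the date stays unknown, every CGM day on which the dose could have fallen is not usable.
3. Have sites apply the test at Visits 3 and 19 from the concomitant-medication record already taken there. Fewer than 4 clean days then triggers the existing repeat course, and the pooling rule in SAP 2.1.3 item 7 works on clean days.
4. Amend Protocol 11.4.2.1 and SAP 2.4.4.1 so that acetaminophen use removes the affected days, and the patient only if fewer than 4 clean days remain. The handling of other prohibited drugs need not change.
5. State that the same rule applies to baseline CGM and to all CGM endpoints.

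The cost is short edits to four sections and one SAP item, a check of the medication record at two visits with intake dates (and times, if the window uses them), and a few more repeat CGM weeks. No new assessment is needed.
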